Joint pain	0	0	0	0
Gas	2	0	0	2
Anorexia	1	1	2	4
Others	2	0	0	2
Summary of symptoms				
Mild	3	3	1	7
Moderate	0	0	1	1
Severe	0	0	0	0
Any symptom	3	3	2	8

Signs and symptoms in outpatient schoolchildren:

Symptoms (%)	Dose(CFU)			
	4 log (n=16)	5 log (n=16)	6 log (n=16)	Placebo (n=22)
Diarrhea	0	0	0	0
Dysentery	0	0	0	0
Loose stools	1	4	2	2
Abdominal pain	4	3	3	3
Headaches	5	2	3	3
Fever	1	0	0	2
Any mild	8	9	6	9
Any moderate	0	1	1	2
Any severe	0	0	0	0

In summary, the school children trials demonstrated SC602 to be well tolerated, with mild symptoms in about half, and moderate symptoms rarely. Loose stools and mild abdominal cramps may occur somewhat more commonly than in controls, though not remarkably so. Secondary transmission of vaccine was not evident.

The combined trials in adults and school children support further efforts to evaluate the vaccine in small numbers of children in the target population age range of 1-5 years. This study is designed towards that end.

Research Plan

STUDY DESIGN

A randomized, double-blind, placebo-controlled clinical trial is proposed, conducted in 4 phases. The first 3 phases will be inpatient trials directed primarily at determining the safety and optimal dose of SC602 in the target age group of 12-35 months old children. Healthy children will be admitted in ICDDR,B Matlab research facility after screening and taking consent. Children will be followed closely for symptoms, fecal shedding of vaccine, and immune markers. After 5 days of observation, they will be treated with an antimicrobial if shedding *Shigella* to truncate intestinal colonization prior to discharge. The volunteers will be requested to come to Matlab on days 14 and 28 for submission of blood and stool specimens. On the basis of these studies, the optimal dose in this age group will be chosen. The outpatient trial will follow, in 12-35 months old children, and providing only the single dose chosen in the inpatient trials, or placebo. The additional intent of the outpatient trial is to assess risk for secondary transmission from vaccine recipients to household contacts. These trials will administer vaccine or placebo to 78 children, and monitor about 100 household contacts for secondary transmission. These studies will form the basis for consideration of further safety and/or efficacy trials of SC602 in this population.

Number of subjects enrolled in the trials

Trial	Vaccine	Placebo	Household contacts	Dose
Inpatient #1	12	6		10(3) or 10(4) CFU

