Inpatient #2	12	6		10(4) or 10(5) CFU
Inpatient #3	12	6		10(5) or 10(6) CFU
Outpatient	16	8	100	To be determined
Totals	52	26	100	

1. Inpatient trial #1:

The first inpatient trial will admit 18 healthy children age 12-35 months of age with a caretaker, to the ICDDR,B clinical treatment and research facility in Matlab, Bangladesh. Baseline stool and serum specimens will be collected for stool culture and

characterization, and fecal and serum immunoglobulin studies. Children will be randomized to 3 dose groups: 6 will receive a single oral dose of 10^3 CFU SC602 with bicarbonate buffer; 6 will receive 10^4 CFU with buffer; and 6 will receive a placebo (sterile water) and buffer. Close daily monitoring of symptoms and physical examination will be conducted. All stools will be collected for culture and characterization. On day 6, all children will be given antimicrobial therapy prior to discharge. Health workers will collect stool and serum specimens for immunoglobulin assay during home visits on days 14 and 28 following vaccination. Secretory IgA specific for *S. flexneri* 2a LPS will be assayed in stool samples. Anti-*S. flexneri* 2a LPS IgA and IgG will be assayed in serum samples.

Inpatient trials data/specimen collection

Study Day	0	1	2	3	4	5	6	14	28
Vaccinate	X								
Symptoms	X	X	X	X	X	X	X		
Stool cx	X	X	X	X	X	X	X		
Stool/Blood for Ig	X							X	X

2. Inpatient Trial #2

Approximately 2 weeks after the 1st trial is begun, the 2nd inpatient trial will again admit 18 children with their caretaker to the ward. The chosen dose(s) will be administered to 12 children (6 each if 2 doses), and placebo to 6. Children will be followed similarly to trial 1. Stool specimens for culture, and stool and serum specimens for Ig studies will be collected according to the same schedule as in the 1st trial.

Interpretation of optimal dose to be administered in the 2nd inpatient trial will be based on analysis of rates of fecal shedding of SC602, and on rates and severity of symptoms demonstrated during follow up in this 1st trial. The possible doses administered in the 2nd trial will be 10^3 , 10^4 or 10^5 CFU.

Inpatient Trial No. 2 Dose Selection Guidelines:

% Shedding Trial 1	Symptoms Trial 1	Dose 1 (CFU)	Dose 2 (CFU)
<34%	Minimal	10^5	-
<34%	Mild	10^4	10^5
<34%	Mod (few subjects)	10^4	-
<34%	Mod (many subjects)	Stop study	-
35-67%	Minimal - mild	10^4	10^5
35-67%	Mod (few)	10^4	-
35-67%	Mod (many) or Severe (any)	Stop study	-
>68%	Minimal-mild	10^4	10^5

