DATA COLLECTION METHODS

Baseline

Baseline socio-demographic data and laboratory specimens will be collected during the week prior to vaccination. The laboratory assays will include serum (about 4 ml), stool and urine for Ig assays; and stool for O&P and culture. Forms for these data are included in appendix.

Follow up

Inpatient trials. Following vaccination, study subjects will be monitored every day until discharge by study physicians. Information to be obtained during follow-up will include vital signs, responses to an interview regarding symptoms experienced by the subject during the last 24 h, and a physical examination of the study subjects. Laboratory follow up will include culture and characterization of all stools each day until discharge. Discharge will be allowed beginning on day 6 if at least 2 sequential stools are culture negative for SC602. All subjects will receive antibiotics on day 6 prior to discharge. For those who are culture positive for the vaccine, they will be retained on the ward until 2 sequential culture negative stools are received, but in no case longer than 10 days after vaccination. If still shedding SC602 72 h after initiating antimicrobial therapy, a different antibiotic will be given, and the first drug discontinued. On days 14 and 28, subjects will be asked to provide stool and serum collection for Ig assays.

Outpatient trial. Following vaccination study subjects will be monitored daily for 5 days by the teams of one physician and one CHW. Information obtained will again include vital signs, physical exam and responses to a symptom interview. Additionally, symptoms occurring in household contacts will also be sought out and recorded. Beginning on day 6, subjects will be visited every other day by a team of one health assistant (HA) and one CHW who will collect data on adverse events in the subjects

and their contacts using a pre-tested questionnaire. After day 10 until conclusion of the study on day 28, these teams will continue to visit vaccinees every 3 days only if the stool is persistently culture-positive for SC602. Teams will visit all vaccinees on days 14 and 28 for stool and serum collection for Ig assays.

Specimens collected

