Inpatient trials: All subjects will be treated with nalidixic acid (55 mg/kg/day orally in 4 divided doses for 5 days) beginning on day 6, and discharged when 2 consecutive stools are negative by culture for *Shigella*. If stools are persistently positive for *Shigella* after 72 h of nalidixic acid therapy, an alternative antibiotic will be chosen. The vaccine strain is sensitive to all standard antimicrobial agents including quinolones, ampicillin and trimethoprim-sulfamethoxazole, all of which are available for use in Matlab. Additionally, for subjects that have symptoms of intestinal infection, medical management will follow standard WHO guidelines, including oral rehydration therapy (ORT) and antibiotics as appropriate. The antibiotic of choice for symptomatic subjects will again be naladixic acid.

Outpatient trial: Vaccinees and household contacts symptomatic of intestinal infection during the study period (28 days of follow up) will be treated according to WHO guidelines as referred to above. Additionally, vaccinees persistently culture positive for *S. flexneri* on day 28 of follow up, will be treated with naladixic acid to terminate intestinal colonization. Household contacts culturing *S. flexneri* from stool samples at any time will also be treated with naladixic acid. Adult household contacts will be treated with a dose of 1 gm orally every 6 h for 5 days; children will be dosed as above.

Oral rehydration therapy will be started as soon as subjects develop significant diarrhea or have signs or symptoms suggestive of volume depletion. Subjects who cannot adequately be rehydrated with oral fluids will be treated with intravenous solution at the ICDDR,B Matlab Hospital.

LABORATORY METHODS

SC602 Shedding:

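### An inpatient can be sent home at the day-10 limit without two negative stools, and no culture is scheduled afterwards

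*Combined protocol and SAP*

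**What the plan says.** Discharge of inpatients is described in two places.

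- Data Collection Methods, Follow up, Inpatient trials: discharge is possible from day 6 with two negative stools. A child positive for the vaccine strain is "retained on the ward until 2 sequential culture negative stools are received, but in no case longer than 10 days after vaccination".
- Medications Used, Antibiotics & ORT, Inpatient trials: all children receive a 5-day course of nalidixic acid "beginning on day 6, and discharged when 2 consecutive stools are negative by culture for" *Shigella*. No day limit appears here.

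Both sections provide for a change of drug. Follow up says: "If still shedding SC602 72 h after initiating antimicrobial therapy, a different antibiotic will be given, and the first drug discontinued". Antibiotics & ORT says that, for stools still positive "after 72 h of nalidixic acid therapy, an alternative antibiotic will be chosen".

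On culture, Follow up says: "Laboratory follow up will include culture and characterization of all stools each day until discharge". The inpatient collection table under Inpatient trial #1 marks stool culture on days 0 to 6 only. For later specimens, Follow up says "On days 14 and 28, subjects will be asked to provide stool and serum collection for Ig assays", and Inpatient trial #1 says "Health workers will collect stool and serum specimens for immunoglobulin assay during home visits on days 14 and 28 following vaccination". Specimens collected likewise assigns those stools to the secretory IgA assay.

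The opening of Study Design gives the purpose of the antibiotic: "to truncate intestinal colonization prior to discharge". The Project Summary states the same intent.

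**The concern.** The limit on ward stay can override the two-negative criterion, and the plan does not say what follows when it does. A toddler last known to be shedding a live strain could go home with clearance unconfirmed. No household contacts are enrolled in the inpatient trials, and this happens before the outpatient trial has examined transmission from this age group. The documents name no later culture that would find a child who stays well but keeps shedding. That departs from the stated intent to end colonization before discharge.

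What is at stake is the safety of that child and household. Dose selection rests on shedding and symptom rates in the ward, where such a child has already been counted as a shedder, so no dose decision changes.

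**Working it through.** The plan gives no figure to reproduce. The check is whether its own timings allow a child to reach the limit without two negatives, and whether any scheduled culture follows.

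**Inputs.** Antibiotic start: day 6. Switch: 72 h later. Limit: day 10 (all from Follow up and Antibiotics & ORT). Eligible stool frequency: 3 per week to 3 per day (Inclusion criteria), so stools are 168/3 = 56 h to 24/3 = 8 h apart. Plates: 24 to 48 h (Laboratory Methods, SC602 Shedding).

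**Time available.** Switch day = 6 + 72/24 = 9. Time on the second drug before the limit = 10 − 9 = 1 day. Time from antibiotic start to the limit = 10 − 6 = 4 days = 96 h.

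**Can two negative stools be passed in time?** The relevant event is passing the stool, not reading the plate, because a ward plate can be read after the child has left.

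- Second drug, best case (a first negative stool right at the switch): the second stool falls on day 9 + interval/24.
- First drug: the latest first negative that leaves room for a second by day 10 is 96 h − interval after the start.
- As an illustration, if stools follow a Poisson process (an assumption), the chance of fewer than two in the 24 h after the switch is e^(−m)(1 + m), where m is the expected number.

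| Frequency | Interval | Second stool after day-9 switch | Fewer than two stools in 24 h | First drug: latest first negative |
|---|---|---|---|---|
| 3 per day | 8 h | 9 + 8/24 = day 9.33 | m = 3: 0.20 | 96 − 8 = 88 h |
| 1 per day | 24 h | 9 + 24/24 = day 10.0 | m = 1: 0.74 | 96 − 24 = 72 h |
| 3 per week | 56 h | 9 + 56/24 = day 11.33 | m = 3/7: 0.93 | 96 − 56 = 40 h |

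A child who clears promptly on the first drug will normally pass two negatives by day 10. A child who needs the second drug may not. If the switch waits until the 72-h stool is read, it moves to day 9 + 1 to 9 + 2 = day 10 to 11, at or past the limit. If the limit runs to the end of day 10 (day 11.0), a child passing 3 stools a week still misses it after a day-9 switch.

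**What follows discharge?** The text ends culture at discharge and the table ends it at day 6. Days 14 and 28 are for immunoglobulins. Scheduled cultures after a day-10 discharge: 0.

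**How many children?** The documents give no treatment-failure rate and no shedding rate for this age group. Earlier data span 0/5 shedding (Matlab adult inpatients at 10^4 CFU) to 12/12 (US inpatients at 10^4 CFU). No count follows from these.

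**The case against.** **The two sections do not conflict.** A reader might infer that they give opposite orders for a child still positive on day 10. The text does not support that: Antibiotics & ORT is silent on a limit and nowhere orders a longer stay, so the explicit limit in Follow up can be read as completing it. This objection stands, and a cross-reference is enough. It does not remove the gap, which arises precisely when the limit applies.

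**Unread is not unverified.** A reader might require both negatives to be readable by day 10 and conclude that most slow stool-passers fail. That discounts plates still incubating at discharge, which can be read 24 to 48 h later. This also stands, and it narrows the affected group to children who have not passed two consecutive negative stools.

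**Other safeguards exist.** Study subjects with intestinal illness are to be cultured, and an outbreak of symptomatic diarrhea with SC602 isolated in vaccinees' baris stops the study. But the illness rule sits in the outpatient text, and both rules depend on symptoms, so neither finds a well shedder.

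**The plan accepts shedding at home.** Outpatient vaccinees may shed until day 28. They do so after Safety Monitoring Committee review, at one chosen dose, with contacts followed, repeat cultures for positives, and treatment at day 28. An inpatient discharged at the limit has no such follow-up.

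**The remedy is late.** Day 14 may fall during treatment, so the first clean check may be day 28, 18 days after discharge. That is partly right, but a positive on day 14 would still be informative and could be acted on.

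**Conclusion.** The point holds as a minor gap with a cheap remedy. The plan allows discharge at day 10 without two negative stools, schedules no culture afterwards, and so can fall short of its own intent to end colonization before discharge. The route is narrow: chiefly a child switched to a second drug on about day 9, with roughly one day left.

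It is probably rare, because every inpatient is treated and the strain is described as sensitive to the standard drugs. A reader might scale up earlier shedding rates to count affected children. The documents do not support this. Adults at 10^4 CFU in Matlab shed in 0/5 cases, so there is no positive floor. High shedding in the second trial with minimal or mild symptoms leads straight to the outpatient trial, so a full three trials of universal shedders is not a realistic ceiling. The number may be zero.

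A reader might also infer harm to the shedding-duration outcome. Shedding after such a discharge would go unseen, but treatment on day 6 already cuts natural duration short in the inpatient trials. The matter is one of safety. The existence of the gap rests on the text alone; only the illustration of reachability uses assumptions about stool timing.

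**What to change.** 1. In both Follow up and Antibiotics & ORT, state one rule: discharge after two consecutive culture-negative stools, or on day 10 at the latest.
2. Read all ward plates still incubating at discharge.
3. If a child's ward stools, including those plates, do not show two consecutive negatives, complete the antibiotic at home, culture both the day-14 and day-28 stools already being collected, and re-treat if either is positive.
4. Add these conditional cultures to the inpatient collection table.

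Both days are needed. If a second course also lasts 5 days (an assumption), a day-9 switch ends on day 9 + 5 = 14 and a day-11 switch on day 16, so a negative on day 14 may only reflect ongoing treatment. Day 28 is then 12 to 14 days after the end of treatment.

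The cost is a wording amendment and up to two cultures per affected child, with no new visit or specimen for the scheduled cultures and no longer ward stay. The drawback is that a day-28 culture is read on day 29 to 30, so any re-treatment needs a contact just after the last scheduled visit.

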1. Oral administration of SC602 to healthy Bangladeshi children from 12 to 35 months of age in dose levels less than or equal to 10^6 CFU will not lead to significant adverse events.
2. The dose that consistently colonizes vaccine recipients and is safe, will also induce evidence of immune stimulation.
3. There may be some secondary spread of vaccine to household contacts of vaccine recipients, but there will be no vaccine-induced occurrence of dysentery/diarrhea.

Specific Aims

1. To evaluate adverse events associated with oral administration of up to 4 dose levels of SC602 [10^3 , 10^4 , 10^5 or 10^6 CFU] relative to placebo in healthy children 12-35 months of age in a community endemic for *Shigella*.
2. To evaluate duration of fecal shedding of SC602 in these children for up to 28 days after vaccination.
3. To evaluate probability of, and symptoms associated with, secondary spread of SC602 to household contacts of vaccinated children as determined by stool culture of these contacts for the vaccine strain.
4. To evaluate humoral immune responses in serum and stool, manifested by changes in immunoglobulins.

Background of the Project

Epidemiology.

The 4 species of the genus *Shigella* are the most common bacterial cause of severe bloody diarrhea (bacillary dysentery) worldwide. In the developing world, *Shigella flexneri* predominates, with *S. flexneri* 2a specifically the predominant serotype. Studies from the Matlab, Bangladesh field research station of the ICDDR,B reveal that in 8-10% of all deaths in 1-4 year old children are due to bloody diarrhea. Stool cultures from subjects with diarrhea (all clinical variants) in this population reveal shigellae in 8-12% of specimens; about 60% of which are *S. flexneri*. In a community-based cohort study of 700 <5 years old children in this area, the attack rate of *Shigella*-

associated diarrhea was 25 episodes per 100 child-years, and 15 episodes per 100 child-years for *S. flexneri* (Baqui et al, 1992). Globally, 65% of *Shigella* cases occur in children <5 years old. In the developing world, overall, 60% of cases are associated with *S. flexneri*, with 32-58% being the *S. flexneri* 2a serotype. *S. sonnei* predominates in the developed world (77% of isolates) (Kotloff et al, unpublished). The incidence of clinical shigellosis peaks at 1-4 year old children and decreases to approximately 25% of peak levels in older children and adults living in endemic areas (Keusch et al, 1991; Slayers et al, 1994).

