>68%	Mod (few)	10^3	10^4
>68%	Mod (many) or Severe (any)	Stop study	-

3. Inpatient Trial #3:

If considered to be necessary based on the absence of significant fecal shedding/symptoms in 10^5 CFU recipients, then a 3rd inpatient trial of 10^6 CFU will commence. The design will be identical to the earlier trials, though 10^5 and/or 10^6 CFU will be given to 12 subjects, and placebo to 6. Baseline studies and follow up procedures will be identical. The optimal dose to be administered in the outpatient trial will be determined from the combined data from the inpatient trials.

Inpatient trial No. 3 dose selection guidelines:

% Shedding Trial 2	Symptoms Trial 2	Dose 1	Dose 2
<34%	Minimal	10(6)	-
<34%	Mild	10(5)	10(6)
<34%	Moderate (few)	10(5)	-
34-67%	Minimal-mild	10(5)	10(6)
34-67%	Mod (few)	10(5)	
34-67%	Mod (many), or Severe (any)	Proceed to OP trial with 10(4)	
>68%	Minimal or mild	Proceed to OP trial with 10(5)	

4. Outpatient Trial:

The outpatient trial will enroll 24 children from neighborhoods proximal to the clinical facility, vaccinating them approximately 3 weeks after beginning the 3rd inpatient trial. Additionally, household contacts of these children will be recruited and followed for intestinal symptoms and fecal shedding of SC602. Baseline stool and serum specimens will be collected from vaccine recipients, and processed as before.

Children will be randomized into 2 groups; 16 will receive the single best dose of vaccine identified in the inpatient trials (with buffer), and 8 will receive placebo with buffer. Every day for the first 5 days following vaccination, a study physician will visit the children at home, record symptoms and signs of illness, and perform directed physical examination. Symptoms in household contacts will be recorded as well. A health worker will collect stool samples from vaccinees on days 2, 4, 6, 8 and 10 for culture and characterization. If persistently culture-positive for *Shigella flexneri* on day 10, stools will continue to be collected each 3 days until 2 consecutive stools are culture-negative or until day 28, at which time antimicrobial therapy will be administered to truncate intestinal carriage. Household contacts will have stool collected on days 6 and 10 for culture, and will be asked about intestinal symptoms since the last visit. Stool and serum specimens for immunoglobulin assays will be collected on days 14 and 28 from vaccine/placebo recipients.

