Four small trials will be conducted in sequence as part of this protocol. Up to three inpatient trials will be followed by an outpatient trial. The inpatient trials will enroll 18 subjects each, of whom 12 will receive vaccine and 6 placebo. The outpatient trial will enroll 24 subjects, providing vaccine to 16 and placebo to 8. Additionally, as part of assessment for secondary transmission risk, household members will be recruited for participation in a minimal risk aspect of the outpatient trial, collecting only 2 stool samples and symptom responses. No medication or vaccine will be provided to this population, unless symptomatic intestinal disease is apparent and/or the vaccine strain is cultured from their stool. In that case, standard antibiotic treatment will be provided. Assuming 5 household members per vaccinee in the outpatient study, about 100 household members will be enrolled.

As a phase 1 trial in young children, sample size considerations are relatively less important than safety concerns. Our sample size has been determined based on three considerations:

We feel an ethical obligation to perform the trial in as safe a manner as possible. That is why we escalate the dose sequentially in the inpatient studies, providing only the very lowest doses initially, rather than expose all subjects at once. That is also why we expose the fewest number of volunteers possible.

Logistical considerations. How many volunteers are available to participate, and how many can be accommodated and monitored adequately in the facilities at our disposal?

Statistical considerations. With at least 12 volunteers receiving the chosen dose, and

20 placebo, if none of the placebo recipients and a third of the vaccinees experience an adverse event, there will be >80% power to detect this difference with >95% significance level by Fisher Exact Test. Similarly, if none of the placebo recipients sero-convert, and at least one third of the vaccinees at the chosen dose sero-convert, we will be able to detect that difference with >80% power and >95% significance by Fisher Exact Test.

OUTCOME VARIABLES

Clinical

- Adverse events in study subjects.
- Secondary transmission of SC602 to household contacts of vaccinees.
- Adverse events in household contacts of vaccinees.

Laboratory

- Occurrence and duration of fecal shedding of the vaccine strain.
- Immune response as measured by changes in anti-*S. flexneri* 2a LPS secretory IgA in stool, and IgA and IgG in serum.

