The data from the vaccine and placebo groups will be compared to determine: a) whether vaccination was associated with increased occurrence of adverse events; b) the extent of secondary spread of the vaccine strain; c) whether there was any vaccine induced outbreak in a bari or neighborhood; and d) the immune response to the vaccine.

The titer of a serum ELISA is the reciprocal of the last dilution with a positive optical density (OD). To show that an individual has responded to the *Shigella* vaccine, a 3-fold increase in titer over the day 0 serum is required for any subsequent sample. In the primary analysis of stool or serum ELISA data, a significant LPS antibody response will be defined as a 3-fold or higher increase in titer after vaccination. In a secondary analysis, the geometric mean titer plus 3 standard deviations of the day 0 samples will be used as a cutoff for significance of antibody response after vaccination.

Use

Combined assessment of shedding, safety and immunogenicity data will serve as the basis for consideration of further investigation of SC602 in expanded safety and efficacy studies of SC602. If personal and community safety, and immunogenicity are demonstrated, then a subsequent protocol will be considered to further evaluate field protective efficacy and safety in larger numbers of children.

MODIFICATIONS TO/DEVIATIONS FROM THE PROTOCOL

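### Secondary spread is placed under a vaccine–placebo comparison with no estimate, unit or upper limit; zero positive households out of 16 would still allow about 17% household transmission

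*Combined protocol and SAP*

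**What the plan says.** The only analysis sentence on spread is in DATA MANAGEMENT, 2. Analysis: "The data from the vaccine and placebo groups will be compared to determine" four items, of which two are "b) the extent of secondary spread of the vaccine strain; c) whether there was any vaccine induced outbreak in a bari or neighborhood". It names no test, unit, interval or acceptable limit for spread.

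Other sections treat spread differently:

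- Specific Aim 3 is to evaluate the probability of spread to household contacts of vaccinated children, by culturing the contacts' stool for the vaccine strain. Age range and gender says the outpatient trial will focus on transmission.
- Hypothesis 3 reads: "There may be some secondary spread of vaccine to household contacts of vaccine recipients, but there will be no vaccine-induced occurrence of dysentery/diarrhea".
- LABORATORY METHODS has *S. flexneri* isolates from vaccinees and contacts tested by PCR to identify SC602.
- SAMPLE SIZE gives the numbers: "The outpatient trial will enroll 24 subjects, providing vaccine to 16 and placebo to 8", and "Assuming 5 household members per vaccinee in the outpatient study, about 100 household members will be enrolled". Fisher's exact test appears there only for adverse events and sero-conversion.
- DATA MANAGEMENT, Use sets the consequence: "If personal and community safety, and immunogenicity are demonstrated, then a subsequent protocol will be considered". It does not define what would demonstrate community safety.

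**The concern.** Aim 3 asks for one probability in one group: how often SC602 passes from a vaccinated child to the household. The Analysis section attaches a two-group contrast to it. Placebo children receive no SC602, and the strain is identified by PCR, so few or no positives are expected in the 8 placebo households. They therefore carry almost no information on the rate in the other 16.

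The gap matters most if nothing is found, because the plan does not say what a zero count would rule out. The protocol already shows how a zero can be over-read. In the adult outpatient trials SC602 was isolated from no vaccinee and no contact, so transmission from a shedding person was hardly tested. The section on those trials nevertheless concludes that there was no transmission risk. The Project Summary repeats this for adults and school children together, and neither place gives a bound. The same step after the present trial would feed into the decision on a larger study of a live strain.

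**Working it through.** **Inputs.** Outpatient allocation 16 vaccine and 8 placebo; 5 household members per vaccinee; about 100 contacts (SAMPLE SIZE). Two rectal swabs per contact, on days 6 and 10 (Specimens collected). At least half of a household's contacts willing to take part (Inclusion criteria).

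**The plan's own figure.** None is given for spread. The one stated power figure, "there will be >80% power to detect this difference with >95% significance level by Fisher Exact Test", concerns adverse events in 12 vaccinees against 20 placebo recipients. It is reproduced: 2/12 v 0/20 gives p = 0.133 and 3/12 v 0/20 gives p = 0.044, so power is P(X ≥ 3), X ~ Binomial(12, 1/3), = 81.9%. It says nothing about spread.

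**Units available.** At most 16 vaccinee households. Contacts in them: 5 × 16 = 80 at five per household, or 100 × 16/24 = 67 if the stated 100 divide 2:1. (Five per household over all 24 would be 120, so the contact denominator is itself unsettled.)

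**What zero positive households would exclude.** With x = 0 of n = 16, the exact upper limit solves (1 − p)^16 = α:

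- one-sided 95%: 1 − 0.05^(1/16) = 17.1%
- two-sided 95%: 1 − 0.025^(1/16) = 20.6%

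**How often zero would be seen.** P(0 of 16) = (1 − p)^16:

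- true household rate 5%: 0.95^16 = 44.0%
- true household rate 10%: 0.90^16 = 18.5%

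**Per contact.** If contacts were independent, zero positives would give a one-sided limit of 1 − 0.05^(1/80) = 3.7% with 80 contacts, or 1 − 0.05^(1/67) = 4.4% with 67. Contacts of one household share exposure to the same child. If they were fully dependent there would be only 16 independent units and the per-contact limit would be 17.1%. The defensible per-contact limit lies between these extremes, and the plan does not say how it would be placed.

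**Detection.** These limits assume that every infected household is found. If the swabs find a fraction s of them, the household limit becomes 17.1%/s. The documents give no value for s. Purely as an assumed range, s = 0.8 gives 21.3% and s = 0.5 gives 34.1%.

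**The case against.** The case against is that the plan already handles spread directly. Aim 3 and the outcome list refer to contacts of vaccinees, and isolates are identified by PCR. Contact symptoms are attributed only when SC602 is cultured (Safety Monitoring Committee section). A symptomatic outbreak in the *baris* with SC602 isolated stops the study (Measures Taken to Minimize Risk). The Project Summary lists the same four questions without any comparison of arms. This is also a phase 1 study, and further work is only to be considered, on a combined assessment. All of that stands, and it limits the point to how spread is estimated and reported. It does not supply an estimate, a unit or a bound.

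Stronger readings are tempting, and the documents do not support them:

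- **That spread is declared only if half of the vaccinees' households are infected.** A two-sided Fisher test on households with 0/8 on placebo does need 8/16 (p = 0.022; 7/16 gives p = 0.054). But the plan names no test for spread. One-sided, 7/16 suffices (p = 0.033). By contact, ignoring clustering, 8/67 v 0/33 suffices (p = 0.0498). The threshold belongs to an assumed test.
- **That a finding of no spread is nearly assured.** One confirmed isolate in a contact shows spread, and nothing in the plan sets it aside for want of significance. At a 10% household rate, at least one positive household is expected with probability 1 − 0.185 = 81%, under perfect detection. Hypothesis 3 itself allows some spread.
- **That placebo children cannot be a source.** They are not given SC602, but all subjects are gathered together for dosing and come from selected *baris* near the facility, so one could acquire it. Placebo households also remain the comparator for contact symptoms.
- **That a per-contact limit of 3.7% is 4.6 times too tight against 17.1%.** The two limits are on different scales. Since [0.05^(1/80)]^5 = 0.05^(1/16), they are the same bound when contacts are independent. Nor does the plan say that it will assume independence.

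**Conclusion.** The point holds as a mismatch between aim and analysis, with a missing precision statement. The Analysis section puts the extent of spread under a contrast that says little about Aim 3, and the question on which the outpatient trial focuses has no estimate, unit, interval or clustering method. Zero positive households out of 16 would exclude only household transmission above 17.1% (one-sided) or 20.6% (two-sided).

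These limits assume 16 separate vaccinee households, independent of one another, each followed and with perfect detection. Fewer households, or the incomplete detection to be expected from two swabs and partial participation, would raise them. They are averages over all vaccinees; if few vaccinees shed, a zero says less still about spread from a child who does. The documents do not show that the plan would dismiss isolates actually found.

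**What to change.** In DATA MANAGEMENT, 2. Analysis:

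1. Take item b out of the vaccine–placebo comparison.
2. Make the main measure of spread the proportion of vaccinees' households with at least one PCR-confirmed SC602-positive contact, with its exact upper 95% limit. State whether the limit is one- or two-sided, and take as denominator the vaccinee households actually followed (at most 16).
3. Give a per-contact rate with a household-clustered interval as secondary. A variance-based clustered interval has no width when no contact is positive, so say that the exact household limit is reported in that case.
4. Keep placebo households as the comparator for contact symptoms. List any SC602 isolate found in them descriptively, as cross-household spread.
5. Under Use, and wherever community safety is claimed, state the transmission rate that the data exclude and that it assumes perfect detection.

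The cost is a few lines of text and one exact interval, with no added subjects, visits or samples. The downside is a weaker headline: with no events, the trial could claim only that household transmission above about 17% is excluded.
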